### 6.3.12.1.4 OSI

OSI, will be calculated as MAP x FiO2 x 100/SpO2, will be analyzed at each time point and averaged over the first 24 hours post study drug intake using the same model used for the SpO2/FiO2.

Same SAS code displayed in the SpO2/FiO2 analysis will be used.

Time profile plot of mean OSI in the first 24 hours after treatment will be presented by treatment group. OSI at Day 2 will be analyzed using linear mixed model including, treatment, investigational site and gestational age group as fixed effects.

Same SAS code displayed in the SpO2/FiO2 analysis will be used.

Chiesi

Final 1.0

CCD-5633AA1-02

18/July/2018

---

TP-EP.BS-WW-001-05

Effective date: 29 Jul 15

Related to: SOP-EP.BS-WW-002

Page 32 of 46

## Statistical Analysis Plan

According to the protocol, if the discharge home coincides with 36-wks PMA assessment, data are entered once in the eCRF at 36-wks PMA. In this case, data of 36-wks PMA should be used also for discharge summary and analysis.

### 6.3.12.1.5 SpO2

SpO2 values as well as changes from baseline (Day -1) will be summarized by treatment group by means of descriptive statistics at each post-treatment timepoints.

According to the protocol, if the discharge home coincides with 36-wks PMA assessment, data are entered once in the eCRF at 36-wks PMA. In this case, data of 36-wks PMA should be used also for discharge summary and analysis.

### 6.3.12.1.6 Ventilator Settings

MAP, PIP, PEEP values as well as changes from baseline (Day -1) will be summarized by treatment group by means of descriptive statistics at each post-treatment timepoints.

According to the protocol, if the discharge home coincides with 36-wks PMA assessment, data are entered once in the eCRF at 36-wks PMA. In this case, data of 36-wks PMA should be used also for discharge summary and analysis.

### 6.3.12.1.7 BPD incidence, Mortality/BPD incidence, mortality and RDS-mortality

Mortality/BPD incidence at 36-week PMA will be compared by treatment by means of Cochran-Mantel-Haenszel (CMH), adjusting for stratification GA group. Relative risk (RR) and related 95% confidence interval will be provided using a SAS code similar to:

```
PROC FREQ DATA = ...;
  WEIGHT count;
  TABLE factor*treatment*response/relrisk cmh norow nocol nopercent;
RUN;
/*factor=GA group
```

Chiesi

Final 1.0

CCD-5633AA1-02

18/July/2018

---

TP-EP.BS-WW-001-05

Effective date: 29 Jul 15

Related to: SOP-EP.BS-WW-002

Page 33 of 46

## Statistical Analysis Plan

Only GA factor is included since not possible to use the combination of two factors (i.e. too few neonates by site). Please refer to DR report \*/

The incidence of BPD at 36-week PMA will be compared by treatment as for Mortality/BPD incidence. Cases not assessed at 36-week PMA visit won't be imputed. Missing cases won't be included in test statistics computation.

The mortality incidence at 36-week PMA and at Day 28 will be compared by treatment as for Mortality/BPD rate.

RDS-associated mortality incidence through 14 days of age will be compared by treatment as for Mortality/BPD rate.

### 6.3.12.1.8 Rescue surfactant use

The percentage of patients requiring at least one rescue surfactant dose will be compared by treatment group by means of a Fisher's exact test at 5% significance interval. Odds ratio (OR) and related exact 95% CI will be also provided. Patients with pulmonary hemorrhage will be excluded from this summary.

For Fisher's exact test SAS code similar to this will be used:

```
PROC FREQ DATA = ...;
  WEIGHT count;
  TABLE treatment*result/measures riskdiff (CL=(WALD MN)) alpha=0.05
    exact fisher or / alpha=0.05;
  RUN;
/* option riskdiff (CL=(WALD MN)) gives the WALD CI and the CI based on inverting a score test,
as suggested by Miettinen and Nurminen (1985), but can be adapted if deemed appropriate */
```

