6.5 Treatment allocation

A dynamic randomization method will be used to balance the treatment groups by investigational site and gestational age group (i.e. from 24⁺⁰ to 26⁺⁶ weeks and from 27⁺⁰ to 29⁺⁶ weeks). Patients will be centrally assigned to one of the two treatment arms on admission through an IRT system (Interactive Response Technology, combination of voice and web response system and also referred as IVRS/IWRS).

The IRT will allocate the patient to a certain treatment group using the Pocock and Simon minimization algorithm ⁽¹⁹⁾ and assign the study medication kit number corresponding to the patients' treatment group. IRT specifications will be fully described in a specific document. The IRT will also generate a confirmation after every IRT transaction is performed.

The Investigator will call the IRT on admission to receive the patient number, and before treatment administration to randomize the patient and to obtain the medication kit number. Detailed instructions for use of IRT will be provided to the site.

The patient will be identified by a unique number of six digits: the country will be the first digit, the investigational site number will be the second two digits and the following three digits will be the progressive numbering of the patient within each site (e.g. 101001, 101002 etc.).

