12.3.4 Efficacy variables

Arterial Oxygen Saturation and Ventilator settings

SpO₂/FiO₂

- SpO₂/FiO₂ will be analyzed using a linear mixed model for repeated measures (MMRM) including treatment, time point, treatment by time point interaction, investigational site and gestational age group as fixed effects and pre-dose SpO₂/FiO₂ as covariate. The adjusted means in each treatment group, the adjusted mean difference between treatments and their 95% confidence intervals (CIs) at each time point and averaged over the first 24 hours will be estimated by the model.

Time profile plot of mean SpO₂/FiO₂ in the first 24 hours post-treatment will be presented by treatment group.

- SpO₂/FiO₂ will be compared between treatments at the remaining post-treatment time points (i.e., Days 2, 3, 5, 7, 28±2 PNA, at discharge home and at 36 weeks PMA) using mixed model including treatment, investigational site and gestational age group as fixed effects and pre-dose SpO₂/FiO₂ as covariate.
- SpO₂/FiO₂ will be analyzed by subgroups based on ventilator support used.

FiO₂

➤ FiO₂ will be analyzed at each time point and averaged over the first 24 hours post dose using the same model used for the SpO₂/FiO₂. Pre-dose FiO₂ will be used as covariate.

Time profile plot of mean FiO₂ in the first 24 hours after treatment will be presented by treatment group.

- FiO₂ will be compared between treatments at the remaining post-treatment time points (i.e., Days 2, 3, 5, 7, 28±2 PNA, at discharge home and at 36 weeks PMA) using linear mixed model including, treatment, investigational site and gestational age group as fixed effects and pre-dose FiO₂ as covariate.
- Percentage of patients with at least one reading of FiO₂ equal to 0.21 (i.e. at room air) within 24 hours from first intake will be compared by treatment group by means of a Fisher's exact test at 5% significance interval. Odds Ratio (OR) and related exact 95% CI will be also provided.
- The median duration time to reach FiO₂ equal to 0.21 will be compared between treatment groups by the Mann-Whitney U-test.

Respiratory Severity Score

- RSS, calculated from ventilator settings as MAP x FiO₂, will be analyzed at each time point and averaged over the first 24 hours post study drug intake using the same model used for the SpO₂/FiO₂.

Time profile plot of mean RSS in the first 24 hours after treatment will be presented by treatment group.

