- RSS will be compared between treatments at day 2 using linear mixed model including, treatment, investigational site and gestational age group as fixed effects.

Oxygen saturation index

- OSI, will be calculated as MAP x FiO₂ x 100/ SpO₂ and analyzed at each time point and averaged over the first 24 hours post study drug intake using the same model used for the SpO₂/FiO₂.

Time profile plot of mean OSI in the first 24 hours after treatment will be presented by treatment group.

- OSI will be compared between treatments at day 2 using linear mixed model including, treatment, investigational site and gestational age group as fixed effects.

SpO₂

- SpO₂ values as well as changes from baseline will be summarized at any post-treatment time point by treatment group by means of descriptive statistics.

MAP, PIP, PEEP

- MAP, PIP, PEEP values as well as changes from baseline will be summarized at any post-treatment time point by treatment group by means of descriptive statistics.

Duration of ventilation/oxygen use

- The median duration time (days) of invasive mechanical ventilation, oxygenation, non-invasive ventilation will be compared between treatment groups by using the Mann-Whitney U-test.

Mortality and BPD

- Mortality/BPD rate at 36-week PMA will be compared by treatment by means of Cochran-Mantel-Haenszel (CMH), adjusting for stratification factors (i.e. GA group and investigational site). Relative Risk (RR) and related 95% confidence interval will be provided.
- The incidence of BPD at 36-week PMA will be compared by treatment as for Mortality/BPD rate.
- The mortality rate at 36-week PMA and at Day 28 will be compared by treatment as for Mortality/BPD rate.
- RDS-associated mortality rate through 14 days of age will be compared by treatment as for Mortality/BPD rate.

Rescue surfactant use

The percentage of patients requiring at least one rescue surfactant dose will be compared by treatment group by means of a Fisher's exact test at 5% significance interval. Odds ratio (OR) and related exact 95% CI will be also provided. Patients with pulmonary haemorrhage will be excluded from this summary.

Biomarkers of inflammation

Mean values of biomarkers of inflammation (i.e., CXCL8, IL1 β , IL6, TNF- α , MPO) in the tracheal aspirates as well as change from baseline to 24 and day 2 (48 hours) will be summarized by treatment by means of descriptive statistics.

Alveolar-arterial gradient and Oxygenation Index

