### 6.3.12.1.9 Duration of ventilation and oxygen use

The median duration time of invasive mechanical ventilation, oxygenation and non-invasive ventilation will be compared between groups by the Mann-Whitney U-test using SAS code similar to:

Chiesi

Final 1.0

CCD-5633AA1-02

18/July/2018

---

TP-EP.BS-WW-001-05

Effective date: 29 Jul 15

Related to: SOP-EP.BS-WW-002

Page 34 of 46

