### **6.3.12.1.10 Normal breathing patients within 24 hours**

Percentage of patients with normal breathing within 24 hours will be compared by treatment groups by means of a Fisher's exact test at 5% significance interval. Odds ratio (OR) and related exact 95% CI will be also provided.

The median duration time to reach FiO2 equal to 0.21 will be compared between treatments by the Mann-Whitney U-test.

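### Six re-dosing, room-air and duration tests leave out gestational-age group, a minimisation factor the SAP adjusts for elsewhere: a cheap gain in power forgone if gestational age is prognostic, not an error

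*SAP*

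**What the plan says.** Protocol 6.5 describes the allocation: "A dynamic randomization method will be used to balance the treatment groups by investigational site and gestational age group". GA group has two levels, 24+0 to 26+6 and 27+0 to 29+6 weeks. SAP section 5 repeats this.

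The SAP uses GA group in most of its inferential analyses. The SpO2/FiO2, FiO2, RSS and OSI models (SAP 6.3.12.1.1 to 6.3.12.1.4) include it as a fixed effect. The mortality and BPD comparisons (SAP 6.3.12.1.7) are CMH tests "adjusting for stratification GA group". That section drops site and gives the reason: "Only GA factor is included since not possible to use the combination of two factors (i.e. too few neonates by site".

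Six comparisons have no GA term:

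- **Fisher:** rescue surfactant (SAP 6.3.12.1.8, "exact test at 5% significance interval. Odds ratio (OR) and related exact 95% CI will be also provided"; the code crosses treatment with result only) and room air within 24 hours (SAP 6.3.12.1.10).
- **Mann-Whitney:** durations of invasive ventilation, non-invasive ventilation and oxygen (SAP 6.3.12.1.9, "will be compared between groups by the Mann-Whitney U-test"; the only class variable is treatment) and time until FiO2 is "equal to 0.21 will be compared between treatments by the Mann-Whitney U-test".

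Protocol 12.3.4 names the same tests ("ventilation will be compared between treatment groups by using the Mann-Whitney U-test" and "equal to 0.21 will be compared between treatment groups by the Mann-Whitney U-test").

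**The concern.** Minimisation makes the arms nearly equal on GA group. If GA predicts the outcome, the arm difference then varies less from trial to trial than an unstratified test assumes. The test rejects too rarely when there is no effect, and misses more effects when there is one. Stratifying by GA group restores the intended level and recovers the power.

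The SAP gives no reason for leaving GA out of these six tests. Its one sparsity argument concerns site, and in that same place it keeps the two-level GA factor for binary endpoints. The six endpoints serve the main objective on oxygen and ventilatory support (SAP 1.1) and the secondary objective on re-dosing (SAP 1.2).

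Only test power is at stake. Leaving GA out does not itself inflate false positives, and no gain in precision of the odds ratio is claimed.

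**Working it through.** **Inputs from the documents.** 63 neonates per arm, with no power calculation and hence no planned power to reproduce (protocol 12.1, SAP 4); two-sided 5% tests (SAP 6.3.2); two GA groups.

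**Assumed, because the documents are silent.** Outcome rates and durations by GA group; a near-even GA split (31 and 32 babies per arm) with exact balance; a within-group odds ratio of 0.4 or a 0.5 SD shift in duration.

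**Binary endpoints, full enumeration.** Power in %. Fisher is set against the exact conditional test stratified by GA, and chi-square against CMH, so that Fisher's discreteness is not counted as a GA effect.

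| Comparator rates by GA group | Fisher | Exact stratified | Chi-square | CMH |
|---|---|---|---|---|
| 35/35% | 53.0 | 52.5 | 60.4 | 59.9 |
| 40/30% | 52.2 | 52.1 | 59.7 | 59.7 |
| 45/25% | 50.0 | 51.0 | 57.7 | 58.8 |
| 60/20% | 44.7 | 50.9 | 52.5 | 58.6 |

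The gap of roughly 8 points between exact stratified and CMH (58.6 − 50.9 = 7.7 in the last row) is discreteness, not GA.

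*Hand check of the last row, equal GA groups.* An odds ratio of 0.4 turns 60/20% into 37.5/9.1%.

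- Mean difference: 0.400 − 0.233 = 0.167.
- Pooled variance: 0.2163 ignoring GA, 0.1871 within GA. The test's standard error √(2v/63) is 0.0829 or 0.0771.
- The true standard error is 0.0754.
- Power = Φ((0.167 − 1.96 × SE)/0.0754), which is 52.4% ignoring GA and 58.4% stratified. These agree with chi-square and CMH.

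*Size with no treatment effect.* From 35/35% to 60/20%, Fisher falls from 3.3% to 2.2%. CMH stays at 4.9-5.1%, also at sparse rates of 15/5% and 20/10%.

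*Estimate.* The SD of the log odds ratio is larger when stratified: 0.45 against 0.43 crude at 45/25%, and 0.45 against 0.38 at 60/20%.

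**Durations.** With within-group SD 1, GA shift s and equal groups, the total variance is 1 + s²/4. Ignoring GA therefore acts like raising the critical value to 1.96√(1 + s²/4). The non-centrality is 0.5 × √(63/2) × √(3/π) = 2.742. At s = 1.5 the critical value is 1.96 × 1.25 = 2.45, which gives size 1.4% and power Φ(0.292) = 61.5%, against Φ(0.782) = 78.3% stratified. Simulation, Mann-Whitney v van Elteren power in %:

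| Scenario | s = 0.5 | s = 1 | s = 1.5 |
|---|---|---|---|
| Untied | 75.5 v 77.1 | 69.0 v 76.9 | 58.4 v 77.8 |
| 30% tied at zero | 70.9 v 72.6 | 64.1 v 71.9 | 52.5 v 71.6 |
| 30% zeros, early deaths 20%/5% by GA | 61.6 v 62.4 | 54.2 v 59.8 | 43.2 v 57.4 |
| 30% zeros, early deaths 30%/5% by GA | 58.3 v 58.7 | 51.2 v 55.4 | 40.3 v 51.4 |

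Subtracting gives 0.4-2, 4-8 and 11-19 points. With no GA effect the pair is 77.7 v 77.4.

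**Time to FiO2 0.21**, with 30% never reaching it and given the worst rank: 74.7 v 76.0, 67.8 v 75.3, 55.1 v 74.6. Dropping those babies gives 39.6 v 42.6, 34.2 v 44.8, 24.3 v 46.6, but the SAP does not say how they are handled.

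**Under simulated minimisation** (20 sites, biased coin 0.8, odds ratio 0.35) the pattern is the same. Fisher v exact stratified is 66.1 v 66.6 at 35/35%, 63.9 v 65.7 at 25/45% and 45.3 v 56.4 at 10/60%. Mann-Whitney v van Elteren is 73.5 v 77.8 at s = 0.8. With a 35/65 GA split the gains are 1.8 points (25/45%) and 3.9 points (s = 0.8).

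**A limit on the size statement for rescue use.** Babies with pulmonary haemorrhage are excluded after randomisation (SAP 6.1.4.9). With equal exclusions (15/5% by GA) and no rescue effect, Fisher's size is 3.4-3.8% and CMH's 5.0-5.1%. Suppose instead that exclusions are 5/2% in one arm and 20/8% in the other, and three times likelier in babies needing rescue. The sizes are then 5.2% and 6.3%; at 5/2% against 25/10% they are 7.0% and 7.9%. Stratifying does not cure that.

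**The case against.** The strongest reply is that this is a preference. The tests are valid, the protocol specifies them, and an exploratory study without a power target cannot miss one. All of that is true, and it is why the point is minor.

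Nor can the documents show that any loss exists. They tie RDS incidence to prematurity (protocol section 1) but give no re-dosing or ventilation outcomes by GA group. The re-dosing FiO2 thresholds differ by GA group (protocol 7.1), which makes some link plausible. The entry thresholds differ too (protocol 4.2), so neither size nor direction follows. This stands: the figures are a range, not an estimate.

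For the binary endpoints the gain is about zero unless GA is strongly prognostic; 60/20% is a six-fold odds gradient (1.5/0.25). At an odds ratio of 0.6, Fisher v exact stratified is 18.2 v 19.1 at 45/25% and 14.2 v 18.3 at 60/20%, so power is low either way. The better case is the four rank tests, and their largest gains need a 1.5 SD shift.

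SAP 6.1.4.9 names two windows for rescue use, so seven tests could be counted. SAP 6.3.12.1.8 describes a single comparison, so six is the fair reading.

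The change also has real costs, set out with the fix. They call for labelling and for naming the reference test in advance. They do not outweigh the gain.

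**Conclusion.** The point holds as a minor missed efficiency. The plan balances on GA group and adjusts for it elsewhere, then ignores it in six tests without a reason.

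The trade is lopsided. Stratifying costs about half a point or less if GA is irrelevant. If GA is strongly prognostic, it recovers about 6 points on the binary endpoints and 11-19 on durations. For weak to moderate effects the gain is 0-1 point on the binary endpoints; for durations it is 0.4-2 points at a 0.5 SD shift and 4-8 at 1 SD.

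These sizes rest on the assumed GA effects, the assumed treatment effects (odds ratio 0.4, 0.5 SD) and near-even, balanced GA groups. That false positives are not inflated for rescue use also requires that the haemorrhage exclusion does not differ by arm. The principal oxygenation models and the mortality/BPD tests are unaffected, since they already adjust for GA.

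**What to change.** Before unblinding:

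- In SAP 6.3.12.1.8, and for the proportion at room air in 6.3.12.1.10, add a CMH test stratified by GA group with a common odds ratio and 95% CI. Use the exact stratified test if expected counts are small. Fix the cut-off in the SAP and judge it on totals pooled over arms, so that the choice does not depend on the treatment comparison.
- In SAP 6.3.12.1.9, and for time to FiO2 0.21 in 6.3.12.1.10, add a van Elteren test stratified by GA group.
- Name the GA-stratified test as the reference for each endpoint, report the protocol's Fisher and Mann-Whitney results as supportive, and record the change from protocol 12.3.4.

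This costs some SAP wording and a few lines of SAS. Three consequences should be stated. The stratified odds ratio is conditional on GA, differs from the crude one and has a wider interval. The Hodges-Lehmann interval in the SAP code remains unstratified and should be labelled descriptive, since it may disagree with the van Elteren p-value. Each endpoint carries a second p-value under a plan that tests everything at 5%, which is why the reference must be named in advance.

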### 6.3.12.1.9 Duration of ventilation and oxygen use

The median duration time of invasive mechanical ventilation, oxygenation and non-invasive ventilation will be compared between groups by the Mann-Whitney U-test using SAS code similar to:

Chiesi

Final 1.0

CCD-5633AA1-02

18/July/2018

---

TP-EP.BS-WW-001-05

Effective date: 29 Jul 15

Related to: SOP-EP.BS-WW-002

Page 34 of 46

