| | 
• RDS-associated mortality rate through 14 days of age;• Percentage of patients requiring at least one rescue surfactant dose;• Percentage of patients with at least one reading of $\text{FiO}_2=0.21$ (i.e. room air) within 24 hours from first dosing with test treatment;• Time (hours) to reach $\text{FiO}_2=0.21$ (i.e. room air);• Duration of invasive mechanical ventilation (days), defined as the time until the first successful extubation lasting more than 24 hours;• Duration of non-invasive ventilation (days), defined by nasal continuous positive airway pressure (nCPAP), Bi-level positive airway pressure (BiPAP), nasal intermittent positive pressure ventilation (NIPPV), high flow nasal cannula (HFNC);• Duration of oxygen alone, defined as receiving supplemental oxygen without invasive or non-invasive ventilator support;• Biomarkers of inflammation: CXCL8, Interleukin 1β (IL1β), Interleukin 6 (IL6), Tumor Necrosis Factor-alpha (TNF-α), myeloperoxidase (MPO), prior to study drug administration, at 24 hours and on Day 2 (48 hours) (in a subgroup of babies who require endotracheal intubation for mechanical ventilation when feasible).• Alveolar–arterial (A-a) Oxygen gradient at 3, 6, 12, 18, 24 hours and day 2 post treatment (in a subgroup of babies who have an arterial access, when feasible)• Oxygenation Index (OI) at 3, 6, 12, 18, 24 hours and day 2 post treatment (in a subgroup of babies who have an arterial access, when feasible) |
| Safety variables | 
• AEs and ADRs• Vital signs (systolic and diastolic blood pressure, heart rate) and SpO₂ during administration• Incidence of major neonatal morbidities (for the list of neonatal morbidities and complications of prematurity see section 10.8)• Hematology and blood chemistry: full blood count (FBC), urea, creatinine and electrolytes (sodium, potassium, calcium, phosphorus), alanine aminotransferase (ALT), aspartate aminotransferase (AST), glucose, C-reactive protein• Immunogenicity assessment will be carried out in one blood sample collected approximately 5 weeks after administration (with a window from 3 to 6 weeks) |

| | |
|--------------------------------|--|
| | 
• Bayley Scales of Infant Development at 24 months (± 3 months) corrected age.• Health status questionnaire (health problems, illnesses, injuries, well-being, diet, respiratory assessment) at 24 months (± 3 months) corrected age. |

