8. EFFICACY ASSESSMENTS

- SpO₂/FiO₂ at 30 minutes, at 1, 3, 6, 12, 18, 24 hours, at Days 2, 3, 5, 7, 28±2 PNA, at discharge home and at 36 weeks PMA.

- Fraction of inspired oxygen (FiO₂) at 30 minutes, at 1, 3, 6, 12, 18, 24 hours, at Days 2, 3, 5, 7, 28±2 PNA, at discharge home and at 36 weeks PMA;
- Respiratory Severity Score (RSS) will be calculated from ventilator setting as FiO₂ x MAP in the 2 days post treatment (at 30 minutes, at 1, 3, 6, 12, 18, 24 hours and on day 2);
- Oxygen Saturation Index (OSI) will be calculated as FiO₂ x MAP x 100 / SpO₂ in the 2 days post treatment (at 30 minutes, at 1, 3, 6, 12, 18, 24 hours and on day 2);
- Arterial oxygen saturation determined by pulse oximetry (SpO₂) at 30 minutes, at 1, 3, 6, 12, 18, 24 hours, at Days 2, 3, 5, 7, 28±2 PNA, at discharge home and at 36 weeks PMA;
- Mean airway pressure (MAP) at 30 minutes, at 1, 3, 6, 12, 18, 24 hours, on Days 2, 3, 5, 7;
- Peak inspiratory pressure (PIP) at 30 minutes, at 1, 3, 6, 12, 18, 24 hours, on Days 2, 3, 5, 7;
- Positive end-expiratory pressure (PEEP) at 30 minutes, at 1, 3, 6, 12, 18, 24 hours, on Days 2, 3, 5, 7
- Alveolar-arterial (A-a) at 3, 6, 12, 18, 24 hours and 2 days post treatment (only in a subgroup of babies when feasible).
- Oxygenation Index (OI) at 3, 6, 12, 18, 24 hours and 2 days post treatment (only in a subgroup of babies when feasible).
- Mortality/BPD rate defined as the incidence of patients who are dead or alive with a diagnosis of BPD at 36-week PMA;
- BPD incidence at 36-week PMA;
- Mortality rate at Day 28 PNA and 36-week PMA;
- RDS-associated mortality rate through 14 days of age, defined as deaths associated with RDS through the first 14 days of life, resulting from severe respiratory failure, from pulmonary hemorrhage if the RDS had not resolved before the development of this complication, or from air leaks that occurred in the presence of severe RDS;
- Percentage of patients requiring at least one surfactant rescue dose;
- Percentage of patients with at least one reading of FiO₂=0.21 (i.e. room air) within 24 hours from first dosing with test treatment;
- Time (hours) to reach FiO₂=0.21 (i.e. room air);
- Duration of invasive mechanical ventilation, defined as the time until the first successful extubation lasting more than 24 hours (days);

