## Statistical Analysis Plan

### STATISTICAL ANALYSIS PLAN

The Statistical Analysis Plan (SAP) details the statistical methodology to be used in analyzing study data and outlines the statistical programming specifications for the Tables, Listings and Figures (TLFs). It describes the variables and populations, anticipated data transformations and manipulations and other details of the analyses not provided in the Clinical Study Protocol (CSP).

The analyses described are based on the final amended CSP Version 4.0, dated, 31/Jan/2018.

The SAP will be finalized prior to database lock and describes the statistical analysis as it is foreseen when the study is being planned. If circumstances should arise during the study rendering this analysis inappropriate, or if improved methods of analysis should arise, updates to the analyses may be made. Any deviations from the SAP after database lock, reasons for such deviations and all alternative or additional statistical analyses that may be performed, will be described in a SAP Addendum.

The 24-months assessment analysis will be described in a separate SAP.

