## Statistical Analysis Plan

- Other: NIPPV-NAVAMODE
- Other: NON-INVNAVA
- Other (refer to Data Review Report for exhaustive list)

Invasive ventilation will include the use of at least one the following ventilatory support:

- High Frequency Oscillatory Ventilation (HFOV)
- HFOV/NAVAMODE
- Synchronized Intermittent Mandatory Ventilation (SIMV)
- Patient Trigger Ventilation (PTV)
- Synchronized Intermittent Positive Pressure Ventilation (SIPPV)
- Other: Intermittent Mandatory Ventilation (IMV)
- Other: A/C (assist/control)
- Other: Pressure Support Ventilation (PSV)
- Other: PPVTHRUETTUBE
- Other: SIMV/NAVA,
- Other: IMV/NAVAMODE
- Other (refer to Data Review Report for exhaustive list).

Note: Low Flow Nasal Cannula use will be summarized under “Oxygen alone”.

Duration of non-invasive and invasive ventilation will be defined as total number of days when neonates received non-invasive and invasive mechanical ventilation, respectively.

Duration of ventilation (invasive and non-invasive) will be calculated as the sum of each period of received ventilation which will be calculated as ventilation end date/time minus ventilation started date/time. A review of these data will be performed during BDRM to specify whether specific adaptations of the algorithm have to be implemented.

To account for missing time in date/time when deriving duration variables, the following approaches will be used:

- Time points with unknown start and/or end times (but where the date is known) will be imputed with a time of 00:00 h or treatment administration time (1st treatment Day 1 only) for the tabulations but will be shown as NK:NK in the listings (where NK = Not Known).

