### ***6.1.4.12 Normal breathing (i.e. at room air) patients within 24 hours***

Percentage of patients with at least one reading of FiO2 equal to 0.21 (i.e. at room air) within 24 hours from first intake will be taken as estimation of normal breathing.

Additionally the median duration time to reach FiO2 equal to 0.21 (normal breathing) will be determined.

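### The SAP replaces the protocol's definition of invasive ventilation duration with a sum of all periods without declaring it, and time to FiO2 0.21 has no stated window and no rule for babies who never reach it

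*SAP*

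**What the plan says.** **Protocol.** The efficacy variables in the protocol outline list "Duration of invasive mechanical ventilation (days), defined as the time until the first successful extubation lasting more than 24 hours". Section 8 repeats it: "defined as the time until the first successful extubation lasting more than 24 hours".

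**SAP.** Section 6.1.4.10 takes both ventilation durations as the "total number of days when neonates received non-invasive and invasive mechanical ventilation, respectively" and gives the algorithm: "Duration of ventilation (invasive and non-invasive) will be calculated as the sum of each period of received ventilation", each period being end minus start. It adds: "A review of these data will be performed during BDRM to specify whether specific adaptations of the algorithm have to be implemented". The SAP introduction says: "The analyses described are based on the final amended CSP Version 4.0, dated, 31/Jan/2018". Section 6.3.12.1.9 names the test: "The median duration time of invasive mechanical ventilation, oxygenation and non-invasive ventilation will be compared between groups by the Mann-Whitney U-test". The output is Table 14.2.9.

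**Time to room air.** SAP 6.1.4.12 says that the median time to reach FiO2 "equal to 0.21 (normal breathing) will be determined", and 6.3.12.1.10 compares it by the Mann-Whitney test. Neither sentence sets a window. The headings of both sections and the title of Table 14.2.2.4 refer to 24 hours, while SAP 6.1.4.2 has FiO2 read up to 36 weeks PMA. SAP 6.3.4 says that missing data are generally not imputed and leaves critical cases to the blind data review meeting.

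**The concern.** The two definitions measure different things. The protocol's stops at the first extubation that holds; the SAP's carries on through every later re-intubation. The SAP says it follows protocol version 4.0 but does not mention the difference. It does explain another departure: in 6.3.12.1.7 it says why site was dropped from the Cochran-Mantel-Haenszel strata. A reader of Table 14.2.9 who has only the protocol would therefore take the result for something it is not. Ventilatory support is part of a main objective (protocol 2.1, SAP 1.1), so the endpoint is not incidental.

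The room-air question is smaller. A baby who does not reach 0.21 has no time. With no imputation, that baby drops out of the test, and the comparison is restricted to a subgroup defined by outcome.

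**Working it through.** There is no stated figure to reproduce: protocol 12.1 says no formal power calculation was done.

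**1. The definitions applied to one baby.** Ventilated on days 0 to 2, extubated, then ventilated on days 7 to 17.
- Protocol: the first extubation lasts 7 − 2 = 5 days, which is more than 24 hours, so duration = 2 − 0 = 2 days.
- SAP: (2 − 0) + (17 − 7) = 12 days.

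**2. Illustrative size.** From the documents: 63 per arm (protocol 12.1), two-sided 5% (SAP 6.3.2), Mann-Whitney test. Everything else is assumed. First period F is log-normal with log-SD 1.0. A second period S, log-normal with median 7 days and log-SD 0.8, follows in the re-intubated share (R = 1), more than 24 hours after extubation. Protocol value = F; SAP value = F + R × S. There were 6,000 simulated trials per row. Entries are the percentages significant in favour of arm A / arm B, shorter being favourable.

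| Median F, A v B (days) | Re-intubated, A v B | Protocol definition | SAP sum |
|---|---|---|---|
| 7 v 7 | 20% v 20% | 2.3–2.6% each side | 2.3–2.6% each side |
| 7 v 7 | 30% v 20% | no difference (F unchanged) | 0.7 / 7.4 |
| 7 v 7 | 40% v 20% | 2.4 / 2.6 | 0.2 / 18.2 |
| 4 v 7 | 20% v 20% | 86.0 for A | 73.6 for A |
| 4 v 7 | 40% v 20% | 85.1 for A | 24.4 for A |

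Repeat runs gave 16.4–18.2% for the third row, and 84.8–86.6% and 23.0–25.1% for the last.

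**3. Sensitivity to the assumptions.**
- Last row, second period of median 4 or 10 days: the SAP sum gives 41.8% or 14.3%.
- Re-intubation 25% v 20%, equal first periods: the SAP sum gives 1.4 / 4.2.
- Protocol 6.2.3 allows a tube placed only for dosing and leaves later support to the investigator, so some babies may have 0 days. If half do and only ventilated babies are re-intubated, the last row becomes 12.7% v 5.1%, and the 18.2% becomes 4.7%. If 0-day babies can also be intubated later, the 18.2% becomes 23.8%.

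**4. Time to FiO2 0.21.** Assume 60% v 40% reach it within 24 hours, with equal times among those who do. The default test then uses about 0.60 × 63 = 37.8 and 0.40 × 63 = 25.2 babies, or 63 of 126. In 4,000 runs it was significant in 5.0% two-sided, which is chance level. Ranking non-reachers last gave 54.6%.

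The planned Fisher test on the 24-hour percentage already picks up this difference. Its approximate power is Φ[(0.20 − 1.96 × √(2 × 0.5 × 0.5/63)) / √((0.6 × 0.4 + 0.4 × 0.6)/63)] = Φ[(0.20 − 0.1746)/0.0873] = Φ(0.29) = 61%. An exact test will have somewhat less.

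**5. Deaths on the ventilator.** If support is recorded as ending at death, the SAP sum gives such a baby the days up to death; the protocol definition gives no value. Assume 20% v 10% die ventilated and survivors have a median of 7 days. The sum then favours the arm with more deaths in 9.2% (v 0.6% for the other arm) when deaths centre on day 2. When they centre on day 14, the figures are 1.0% v 5.4%. The direction depends on timing.

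**The case against.** **Table 14.2.9 is not undetermined.** A reader might infer that two analysts would produce two different tables. The documents do not support that: SAP 6.1.4.10 gives one explicit algorithm, the SAP governs the programming, and only the blind data review can adapt it. Nor is the sum biased. Total time on the ventilator is a legitimate quantity, and counting re-intubation is what it is meant to do. What stands is that the endpoint changed and nobody said so.

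**The sizes are assumed.** This is correct. They run from negligible to large, and the largest need every baby to have a first period of several days.

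**Room air.** A reader might infer that the choice of window could reverse the direction of the comparison. That takes an intermediate cut-off such as Day 7, which no document attaches to this endpoint. The readings the text allows are 24 hours (headings and table title) or all readings to 36 weeks PMA. Within 24 hours, Fisher's test already compares the percentages. What stands is the missing window and the loss of non-reachers.

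**Deaths.** A reader might infer that no rule exists anywhere. That cannot be shown. SAP 6.1.4.10 and 6.3.4 refer these matters to the blind data review, 6.2.3 is worded as if that review had taken place, and its report is not among the documents. One can say only that the protocol and SAP contain no such rule. Ranking deaths worst is also one choice among several, beside ventilator-free days or a competing-event analysis.

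**Weight.** The study is exploratory, mortality and mortality/BPD are tested separately, and Tables 14.2.9 and 14.2.2.4 are outside the Key First Results package. This limits the consequences but does not excuse the mismatch.

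**Conclusion.** The definition conflict holds on the wording alone and needs no assumed rate. The protocol ends the count at the first extubation lasting more than 24 hours, the SAP sums all periods, and the change is neither declared nor justified. Any baby re-intubated after a successful extubation gets a different value, 2 v 12 days in the example. It should be fixed.

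How far the result would move cannot be known from the documents. In the assumed scenarios with earlier extubation and more re-intubation in one arm, the share of significant results falls from 85.1% to 24.4%, or from 12.7% to 5.1% with half the babies at 0 days. With equal re-intubation of 20% it falls only from 86.0% to 73.6%.

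The room-air point is minor: no window is stated, and the default test is restricted to reachers. The absence of a rule for ventilator deaths is also minor, and is conditional on how the end of support is recorded and on a review report not seen here.

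**What to change.** Before unblinding:

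1. Reconcile the two definitions. Record the change from the protocol with its reason, state which definition Table 14.2.9 uses, report the other as a supportive analysis, and give the number re-intubated in each arm.
2. State the window for time to FiO2 0.21. Rank babies who do not reach it in that window after all who do, and report the number reaching it.
3. Show deaths on invasive ventilation per arm beside the duration result. A worst-rank analysis of deaths may be added as a sensitivity analysis.

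If the blind data review has already set such rules, copy them into the SAP. If the database is already locked, the SAP introduction provides an addendum for the purpose.

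The cost is some SAP wording and a few lines of programming; support start and end times, deaths and FiO2 readings are already collected. The downsides: a second definition adds a table, ranking non-reachers last gives no difference in hours over all babies, and a worst-rank analysis mixes mortality with duration and gives no difference in days.
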